### 6.2.3. Pharmacokinetic endpoints

#### Combinations A and F

The following pharmacokinetic analyses will be based on the PK analyses set by treatment group using the data from the combined Phases 1b and 2 (Cohorts A1, A2, A3 and Cohorts F1, F2, F3) and the data from Phase 2 (Cohorts A4, A5, A6, A7, A8, A9, A10).

#### Combinations B, C and D

The following pharmacokinetic analyses will be based on the PK analyses set by treatment group using the data from Phase 1b and from Phase 2 separately and for each combination.

$C_{\text{trough}}$  and  $C_{\text{max}}$  for avelumab for all combinations, utomilumab (for Combination A and D), PF-04518600 (for Combinations B and D), and PD 0360324 (for Combination C) will be summarized descriptively (n, mean, SD, CV, median, minimum, maximum, geometric mean, its associated CV, and 95% CI) by treatment group, cycle, and day. Dose normalized parameters (eg,  $CDN - C_{\text{max}}$ ,  $CDN - C_{\text{trough}}$ ) will be reported as appropriate. The trough concentrations for avelumab, utomilumab, PF-04518600 and PD 0360324 will be plotted for each dose using a box whisker plot by cycle and day in order to assess the attainment of steady state

Pharmacokinetic parameters for avelumab, utomilumab, PF-04518600 and PD 0360324 will be taken from observed values or derived from plasma concentration-time data as described in Section 3.2.2.

Presentation of pharmacokinetic data will include:

- Descriptive statistics (n, mean, SD, %CV, median, minimum, maximum) of plasma concentrations will be presented in tabular form by treatment group, dose level, cycle, day and nominal time. Additionally, similar descriptive statistics will also be generated

for dose-normalized utomilumab (Combination A and D), PF-04518600 (Combination B and D), PD 0360324 (Combination C) pharmacokinetic parameters, if appropriate.

- Pharmacokinetic parameters for avelumab, utomilumab, PF-04518600, and PD 0360324 will be listed and summarized by treatment group/dose level, cycle and study day using descriptive statistics (n, mean, SD, %CV, median, minimum, maximum, geometric mean and its associated %CV, and 95% CI). For  $T_{max}$ , the range (min, max) will also be provided. PK parameters with zero values will be excluded from the calculation of geometric means and its associated %CV. If an inpatient dose escalation or reduction occurs, dose-dependent PK parameters ( $C_{max}$ ) for that patient may be dose-normalized when it is known that the drug exhibits linear PK within the dose range and other PK parameters will be reported as estimated; or may only be included in descriptive statistics and summary plots up to the time of the dose change. In addition, dose-normalized  $C_{max}$  and  $C_{trough}$  parameters will be summarized (as described above) using data pooled across treatment groups in which different utomilumab doses, PF-04518600 doses or PD 0360324 doses were administered, if appropriate.

#### **6.2.4. Population pharmacokinetic endpoints**

Pharmacokinetic and pharmacodynamic data from this study may be analyzed using modeling approaches and may also be pooled with data from other studies to investigate any association between avelumab and utomilumab (Combination A), avelumab and PF-04518600 (Combination B), avelumab and PD 0360324 (Combination C) or avelumab, utomilumab and PF-04518600 (Combination D) or Avelumab (Combination F) exposure and biomarkers or significant safety/efficacy endpoints. The results of these analyses, if performed, may be reported separately.

#### **6.2.5. Biomarker Endpoints**

##### **Combinations A and F**

The following biomarker analyses will be based on the biomarker analysis sets by treatment group using the data from the combined Phases 1b and 2 (Cohorts A1, A2, A3 and Cohorts F1, F2, F3) and the data from Phase 2 (Cohorts A4, A5, A6, A7, A8, A9, A10).

##### **Combinations B, C and D**

The following biomarker analyses will be based on the biomarker analysis sets by treatment group using the data from Phase 1b and from Phase 2 separately and for each combination.

For continuous measurement biomarker results, summary statistics (eg, the mean, standard deviation, median, percent of coefficient of variation, and minimum/maximum levels) will be determined at baseline and on-treatment/end of treatment time points, as appropriate. Appropriate change from baseline measurements will be provided. For discrete measurement biomarkers, frequencies and percentages of categorical biomarker measures will be determined at baseline and on-treatment/post-treatment time points, as appropriate; shift tables may also be provided.

## 6.2.6. Endpoints for immunogenicity data of avelumab and other study drugs

### Combinations A and F

The following analyses of immunogenicity data will be based on the Immunogenicity analysis set by treatment group using the data from the combined Phases 1b and 2 (Cohorts A1, A2, A3 and Cohorts F1, F2, F3) and the data from Phase 2 (Cohorts A4, A5, A6, A7, A8, A9, A10).

### Combinations B, C and D

The following analyses of immunogenicity data will be based on the Immunogenicity analysis set by treatment group using the data from Phase 1b and from Phase 2 separately and for each combination.

Blood samples for avelumab and other study drug immunogenicity testing will be collected as outlined in the “Schedule for Pharmacokinetic Sample Collection” table of the Schedule of Assessments section of the protocol.

Patients will be characterized into different ADA categories based on the criteria defined in Table 14.

**Table 14. Patients Characterized Based on Anti-Drug Antibody Results (ADA Status)**

Category	Definition	Patients at Risk (Denominator for Incidence)
ADA never-positive	No positive ADA results at any time point; ADA-negative patients (titer < cutpoint)	Number of patients with at least one valid ADA result at any time point
ADA ever-positive	At least one positive ADA result at any time point; ADA-positive patients (titer ≥ cutpoint)	Number of patients with at least one valid ADA result at any time point
Baseline ADA positive	A positive ADA result at baseline	Number of patients with valid baseline ADA result
Treatment-boosted ADA	A positive ADA result at baseline and the titer ≥ 8×baseline titer at least once after treatment with avelumab	Number of patients with valid baseline ADA results and at least one valid post-baseline ADA result
Treatment-induced ADA	Patient is ADA-negative at baseline and has at least one positive post-baseline ADA result; or if patient does not have a baseline sample, the patient has at least one positive past-baseline ADA result	Number of patients with at least one valid post-baseline ADA result and without positive baseline ADA result (including missing, NR)
Transient ADA response	If patients with treatment-induced ADA have (a single positive ADA result or duration between first and last positive result <16 weeks) and ADA result at the last assessment is not positive.	Number of patients with at least one valid post-baseline ADA result and without positive baseline ADA result (including missing, NR)
Persistent ADA response	If patients with treatment-induced ADA have duration between first and last positive ADA result ≥16 weeks or a positive ADA result at the last assessment	Number of patients with at least one valid post-baseline ADA result and without positive baseline ADA result (including missing, NR)

ADA: anti-drug antibody, NR = not reportable.

The number and percentage of patients in each ADA category will be summarized.

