### Definition of baseline for immunogenicity analyses

The last available assessment prior to the start of treatment with avelumab is defined as ‘baseline’ result or ‘baseline’ assessment. If an assessment is planned to be performed prior to the first dose of avelumab in the protocol and the assessment is performed on the same day as the first dose of avelumab, it will be assumed that it was performed prior to avelumab administration, if assessment time point is not collected or is missing.

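### Table 14 counts patients with a not-reportable baseline ADA result as at risk of treatment-induced ADA but never as events, which lowers the rate whenever such a patient later tests positive

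*SAP*

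**What the plan says.** SAP section 6.2.6, Table 14, defines the ADA categories and the patients at risk for each.

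- **Treatment-induced ADA, numerator.** First route: "Patient is ADA-negative at baseline and has at least one positive post-baseline ADA result". Second route: "if patient does not have a baseline sample, the patient has at least one positive past-baseline ADA result".
- **Treatment-induced, transient and persistent ADA, denominator (the same for all three).** "Number of patients with at least one valid post-baseline ADA result and without positive baseline ADA result (including missing, NR".
- **Abbreviations.** The footnote reads "ADA: anti-drug antibody, NR = not reportable".
- **Negative.** The never-positive row describes "ADA-negative patients (titer < cutpoint", so being negative requires a result.
- **Nesting.** Transient ADA begins "If patients with treatment-induced ADA have (a single positive ADA result or duration between first and last positive result <16 weeks" and persistent ADA is "If patients with treatment-induced ADA have duration between first and last positive ADA result ≥16 weeks or a positive ADA result at the last assessment". Both are subsets of treatment-induced ADA.

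The definition of baseline for immunogenicity analyses (section 3.4.1) is "The last available assessment prior to the start of treatment with avelumab is defined as ‘baseline’ result or ‘baseline’ assessment". It has no rule for a result that is not reportable. Section 4.3.4 admits patients to the immunogenicity sets on the basis of samples collected, so an NR baseline does not exclude anyone.

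**The concern.** The numerator is written in terms of a sample and the denominator in terms of a result. A patient whose baseline sample was taken but gave no reportable result lies between the two. That patient is not negative and does have a sample, so neither route to treatment-induced ADA is open, however many positive results follow. The denominator nevertheless names this state explicitly.

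A rate whose denominator holds patients who cannot enter its numerator is not a clean incidence. The classification also feeds later analyses. Time to and duration of ADA response (section 6.2.6.1), the duration-by-titer cross tabulation (6.2.6.2) and the before-and-after PK analysis (6.2.6.3) are all restricted to treatment-induced ADA. The second PK contrast in 6.2.6.3 sets treatment-induced ADA against never-positive or baseline-positive patients, and this patient is in neither group.

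**Working it through.** The SAP gives no ADA incidence and no NR frequency, so there is no figure to reproduce. The check has three steps.

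**1. Apply Table 14 literally to a patient with at least one positive post-baseline result.**

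| Baseline state | In the three denominators? | Can be treatment-induced? |
|---|---|---|
| Negative | yes | yes (first route) |
| No sample | yes | yes (second route) |
| Sample taken, NR | yes | no |
| Positive | no | no |

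NR is the only state that is at risk without being able to be an event. Such a patient is ADA ever-positive but not baseline positive, treatment-boosted, treatment-induced, transient or persistent.

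**2. Expected size.** Let p be the share with a positive post-baseline result among patients without a positive baseline, assumed equal in NR and other patients. Let f be the NR share of the denominator. Only the fraction 1 − f can be counted, so

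reported incidence = p × (1 − f).

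Both inputs are assumptions:

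| p | f = 0 | f = 2% | f = 5% | f = 10% | f = 20% |
|---|---|---|---|---|---|
| 10% | 10.0% | 9.8% | 9.5% | 9.0% | 8.0% |
| 20% | 20.0% | 19.6% | 19.0% | 18.0% | 16.0% |
| 30% | 30.0% | 29.4% | 28.5% | 27.0% | 24.0% |

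The relative loss equals f. For p = 20% and f = 10%: 0.20 × (1 − 0.10) = 0.18, a loss of 2 points.

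**3. Effect of one affected patient, once it occurs.** Compared with counting that patient as an event, the shift is 1/20 = 5.0 points with 20 at risk and 1/12 = 8.3 points with 12 at risk. Section 5.1 uses 20 as a Phase 2 cohort size and 12 as the maximum per dose level in Combinations B and D.

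Take 20 at risk and 5 with a post-baseline positive, one of whom is the only NR baseline:

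- Table 14 as written: 4/20 = 20.0%
- NR admitted to the numerator: 5/20 = 25.0%
- NR removed from the denominator: 4/19 = 21.1%

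The written rule is below both consistent versions. (If no other patient is an event, removing NR leaves the rate at zero either way.) For transient and persistent ADA, admitting the patient to the numerator raises whichever of the two the patient's results satisfy. Removing NR from the denominator raises each rate that is not zero.

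**The case against.** **A consistent reading is available.** The denominator puts missing and NR side by side, which suggests that the authors meant to treat them alike, and a programmer might take no sample to mean no usable result. The last available assessment could also be read as an earlier valid pre-dose sample, where one exists. This makes loose drafting the likely cause, but it does not close the gap. The denominator lists missing and NR as separate states, other rows of the table refer to a valid baseline result when that is meant, and nothing in sections 3.4.1 or 4.3.4 turns an NR result into an absent sample. Two programmers could derive different counts from the same row.

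**The size is easily overstated.** A reader might infer that ADA incidence in this trial is understated, or that shifts of 5 to 8 points are to be expected. The SAP supports neither. Those shifts are conditional on an affected patient. With p = 20% and f = 10% the expected number of affected patients is 20 × 0.10 × 0.20 = 0.4 in a cohort of 20, and 0.24 in 12.

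**The true rate is unknown.** A reader might also take the wider numerator as the truth and the difference as bias. An NR baseline does not exclude pre-existing antibodies, so counting the patient as treatment-induced could overstate incidence. What can be shown is inconsistency with either coherent definition, not bias against a known rate.

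**The patient is not lost from immunogenicity reporting.** The patient remains ADA ever-positive, is in the overall maximum-titer summary (6.2.6.2) and is in the first PK contrast, ever-positive against never-positive (6.2.6.3). The endpoint named in section 3.2.3 is ADA levels, and no ADA hypothesis or decision rule appears in section 5.1. This objection stands and limits the importance of the point.

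**Conclusion.** The mismatch is real on the wording of Table 14, and its effect is conditional. Whenever a patient with an NR baseline has a later positive result, the patient is counted at risk for treatment-induced, transient and persistent ADA but as an event for none of them. The written treatment-induced rate is then below what either consistent definition would give, apart from the zero-event case noted above. The expected relative loss equals the NR share of the denominator, provided NR patients share the common rate. No NR rate is given, and if there are no NR baselines nothing changes. The consequence is confined to descriptive summaries and to the analyses restricted to treatment-induced ADA, so this is a minor correction worth making because it is cheap.

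**What to change.** Reword the second route in the treatment-induced row along these lines: *or, where the baseline ADA result is missing or not reportable, one or more results after baseline are positive*. This matches the denominator as it stands and also removes the slip in the present wording, which says past-baseline. Transient and persistent ADA, and the analyses in 6.2.6.1 to 6.2.6.3 that depend on treatment-induced status, then follow without further edits.

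The drawback is that an NR-baseline patient with pre-existing antibodies would be counted as treatment-induced. The plan already accepts that risk for patients with no baseline sample. If the sponsor prefers not to extend it, the equally consistent alternative is to remove NR from the three denominators. That leaves such patients out of these rates and out of the treatment-induced analyses, which should then be stated.

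Either change costs a few words in Table 14 and one condition in the ADA program. No data collection changes.

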#### **6.2.6.1. Time to and Duration of ADA response**

The ADA analyses described below will include patients with treatment-induced ADA.

Time (weeks) to ADA response is defined as:

$$(\text{Date of first positive ADA result} - \text{date of first dose of avelumab} + 1)/7.$$

Time to ADA response will be summarized using simple descriptive statistics (mean, SD, median, min, max, Q1, Q3).

Duration (weeks) of ADA response is defined as:

$$(\text{Date of last positive ADA result} - \text{date of first positive ADA result} + 1)/7.$$

Duration of ADA response will be censored if:

- the last ADA assessment is positive AND patient is ongoing treatment with avelumab, or
- the last ADA assessment is positive AND patient discontinued treatment with avelumab.

Kaplan-Meier estimates (product-limit estimates) will be presented together with a summary of associated statistics including the median ADA response time with 2-sided 95% CIs. ADA response rates at different timepoints will be estimated with corresponding 2-sided 95% CIs. The CIs for the median will be calculated according to Brookmeyer and Crowley (1982) and the CIs for the survival function estimates will be derived using the log-log transformation according to Kalbfleisch and Prentice (2002) (conftype=loglog default option in SAS Proc LIFETEST) with back transformation to a CI on the untransformed scale. The estimate of the standard error will be computed using Greenwood's formula.

Duration of ADA response will be displayed graphically and analyzed using Kaplan-Meier methodology. If the number of patients with ADA response is small, the Kaplan-Meier method may not provide reliable estimates. In this case, only descriptive statistics or listings will be provided

#### **6.2.6.2. ADA titer**

For patients who are ADA ever positive, the maximum observed ADA titer for a patient will be summarized, overall and by ADA subcategories (baseline ADA positive, treatment-boosted ADA, treatment-induced ADA, transient ADA response, persistent ADA response) of patients having each discrete maximum titer value will be tabulated. The denominator to calculate the percentages will be the total number of patients in the associated ADA subcategory.

For patients with treatment-induced ADA, a cross tabulation of duration of ADA response and maximum ADA titer will be provided. The following categories for duration of ADA response will be used:  $\leq 1$ ,  $>1$  to  $\leq 3$ ,  $>3$  to  $\leq 5$ ,  $>5$  to  $\leq 7$ ,  $>7$  to  $\leq 13$ ,  $>13$  to  $\leq 16$ ,  $>16$  to  $\leq 25$ ,  $>25$  weeks. In this categorization, the censoring in duration of ADA response is ignored.

### 6.2.6.3. Analysis of PK by immunogenicity status

The following ADA status will be used for the analyses described below.

ADA

- ADA ever-positive versus ADA never-positive
- ADA: treatment-induced ADA versus ADA never-positive or baseline ADA positive

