#### PK parameters and immunogenicity status

The following analyses will include patients in both the immunogenicity analysis set and in the PK parameter analysis set. The PK endpoints pertinent to the immunogenicity analyses are  $C_{\text{trough}}$  and  $C_{\text{max}}$ . Blood samples for avelumab, utomilumab, PF-04518600, and PD 0360324 PK will be collected as outlined in the “Schedule for Pharmacokinetic Sample Collection” table of the Schedule of Assessments section of the protocol.

$C_{\text{trough}}$  and  $C_{\text{max}}$  will be summarized descriptively (n, mean, SD, CV, median, minimum, maximum, geometric mean, its associated CV, and 95% CI) by nominal time and ADA status. Linear-linear plots of mean and median for  $C_{\text{trough}}$  and  $C_{\text{max}}$  over nominal time and by ADA status will be presented.

Among patients with treatment-induced ADA, analyses will be conducted to assess whether  $C_{\text{trough}}$  and  $C_{\text{max}}$  have any changes before and after the first positive ADA assessment. To be included in this analysis, patients must have the same PK parameter available both before and after the first positive ADA assessment. Relative PK day will be calculated as:

$$(\text{PK assessment nominal day}) - (\text{first positive ADA assessment nominal day}).$$

Nominal day is the protocol scheduled timing for an assessment. For example, if  $C_{\text{trough}}$  is collected on Day 1 of Cycle 2 and the first positive ADA result is observed on Day 1 of Cycle 3, then the relative PK day for this  $C_{\text{trough}}$  is -28. Linear-linear plots of mean and median for  $C_{\text{trough}}$  and  $C_{\text{max}}$  over relative PK day will be presented.

CCI

CCI

CCI

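### The treatment-induced ADA contrast for PK places treatment-boosted patients in its reference group

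*SAP*

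**What the plan says.** SAP Section 6.2.6.3 sets two ADA groupings for the descriptive summaries of Ctrough and Cmax: "ADA ever-positive versus ADA never-positive" and "ADA: treatment-induced ADA versus ADA never-positive or baseline ADA positive". It adds a comparison of exposure before and after the first positive ADA result, limited by the words "Among patients with treatment-induced ADA, analyses will be conducted to assess whether" to treatment-induced patients.

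The categories come from Table 14:

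- Baseline ADA positive: "A positive ADA result at baseline", with no exception for patients who are later boosted.
- Treatment-boosted: "A positive ADA result at baseline and the titer ≥ 8×baseline titer at least once after treatment with avelumab".
- Treatment-induced: "Patient is ADA-negative at baseline and has at least one positive post-baseline ADA result", or a positive post-baseline result where there is no baseline sample.

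Section 6.2.6.2 reports treatment-boosted ADA as its own subcategory in the titer summary. Section 6.2.6.3 does not use that category.

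**The concern.** Setting treatment-induced patients apart from baseline positives is useful mainly for seeing whether antibody formed on treatment goes with lower exposure. A titer rise of at least 8-fold is the SAP's own marker of an on-treatment response in patients who started positive. The second grouping nevertheless counts those patients with the ones who showed no such response. If boosted antibody lowers Ctrough or Cmax, the reference is pulled down and the contrast understates the effect. What is at stake is the reading of a descriptive secondary summary. No hypothesis test, error rate or decision rule depends on it.

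**Working it through.** **Where boosted patients fall.** This follows from the definitions alone.

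1. Boosted requires a positive baseline, so boosted is a subset of baseline ADA positive.
2. Treatment-induced requires a negative or missing baseline, so no boosted patient can be treatment-induced.
3. Grouping 2 sets treatment-induced against never-positive plus baseline positive. By steps 1 and 2, boosted patients must be in the reference.
4. Grouping 1 sets ever-positive against never-positive. Boosted patients are on the positive side, together with unboosted baseline positives and treatment-induced patients.
5. The before/after analysis requires the same PK parameter on both sides of the first positive ADA result. Section 3.4.1 takes the ADA baseline before the first avelumab dose. A boosted patient is already positive then, has no earlier avelumab PK, and generally cannot qualify. Cohort A9, where utomilumab comes first, is a possible exception.

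**Size in grouping 2.** The SAP states no figure to reproduce. The inputs below are assumptions: R is the true geometric mean ratio of treatment-induced to unaffected patients, f is the boosted share of the reference, and boosted patients have the same log-scale effect as induced patients.

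- Log geometric mean, unaffected patients: m
- Log geometric mean, induced patients: m + ln R
- Log geometric mean, reference: (1 − f)·m + f·(m + ln R) = m + f·ln R
- Observed ratio: exp[(1 − f)·ln R] = R^(1 − f)

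For R = 0.70, ln R = −0.3567. At f = 5%: 0.95 × (−0.3567) = −0.3388, ratio 0.713. At f = 20%: 0.80 × (−0.3567) = −0.2853, ratio 0.752.

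| R | f = 1% | f = 5% | f = 10% | f = 20% |
|---|---|---|---|---|
| 0.50 | 0.503 | 0.518 | 0.536 | 0.574 |
| 0.70 | 0.703 | 0.713 | 0.725 | 0.752 |
| 0.80 | 0.802 | 0.809 | 0.818 | 0.837 |

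With 20 patients in the reference, f = 5% is 1 boosted patient and f = 20% is 4.

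**How often a boosted patient would occur.** Planned Phase 2 cohort sizes in Section 5.1.1 include 20 to 35 patients. Boosted prevalence is not given; assume 1% to 5%. The chance of at least one is 1 − (1 − p)^n, and the expected number is n·p.

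- n = 20, p = 1%: 1 − 0.99^20 = 0.18; expected 0.2
- n = 35, p = 5%: 1 − 0.95^35 = 0.83; expected 1.75

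**Whether grouping 1 fills the gap.** If a share g of the ever-positive patients are unboosted baseline positives with no effect on exposure, the same algebra gives R^(1 − g). R = 0.70 then reads 0.725 at g = 10%, 0.765 at 25% and 0.837 at 50%. Grouping 1 has no boosted patients in its reference, but its positive side is mixed.

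**The case against.** The strongest reply is that grouping 2 is a complete split of patients who newly seroconverted against everyone else. Section 6.2.6.3 states no purpose for it and never calls the reference unaffected. Section 6.2.6.1 has the same treatment-induced focus for time to and duration of ADA response. Boosted patients are counted in Table 14 and in the titer summary, so a reader can see whether any exist. If there are none, nothing changes. The summaries are by nominal time, so any distortion could appear only at time points after boosting. All of this stands, and it limits the importance of the point. It does not change where boosted patients are placed.

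A reader might infer that every PK-by-ADA analysis is diluted. The SAP does not support that. Grouping 1 keeps boosted patients out of its reference, so their exposure is not lost from the plan.

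A reader might also take the before/after analysis as faulty for omitting boosted patients. The omission follows from anchoring on the first positive result. It does not bias the estimate in treatment-induced patients; it limits whom that analysis covers.

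**Conclusion.** The misplacement is certain whenever a treatment-boosted patient exists, because it follows from the Table 14 definitions. A bias toward no difference in grouping 2 follows only if boosted antibody lowers exposure. Its size cannot be taken from the SAP. Under the stated assumptions it is slight at low boosted shares (0.70 read as 0.713 at 5%) and visible at high ones (0.752 at 20%). Large distortions would need many boosted patients or a very strong effect on exposure, and the SAP gives no evidence of either. Neither planned grouping isolates on-treatment antibody response: grouping 2 has boosted patients on the wrong side, and grouping 1 mixes them with unboosted baseline positives. This is a cheap improvement to a descriptive secondary summary.

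**What to change.** In Section 6.2.6.3, redefine the second grouping so that treatment-induced or treatment-boosted patients are compared with never-positive patients and baseline-positive patients without boosting. Alternatively, keep treatment-induced as it is and show boosted patients in a separate column outside the reference.

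The cost is a wording change and one flag built from a category that the SAP already derives. No new data are needed. The first option pools two kinds of antibody response. The version history records removal of the listing that linked immunogenicity to PK data, so it should not be relied on to separate them again. The second option may show a very small extra group. Under either option unboosted baseline positives stay in the reference, and their antibodies could also affect exposure; grouping 1 remains the contrast with an all-negative reference. Leave the before/after analysis as it is.
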